### 10.2.1.7 Hospital Anxiety and Depression Scale (HADS) score variables

The HADS questionnaire is filled out by subjects at Visits 1, 4, and every 3 months until EOS Visit or Early Discontinuation Visit.

The HADS assessment consists of 14 items that are each scored on a 4-point scale ranging from 0 to 3, with a higher score corresponding to worse anxiety or depression. The depression and anxiety scores will be calculated by summing the scores for the items corresponding to each subscale, as described in the Hospital Anxiety and Depression Scale Manual (Snaith and Zigmond, 1994): the depression score is calculated as the sum of all even-numbered items; the anxiety score is calculated as the sum of all odd-numbered items. Scores for each subscale range from 0 to 21, with higher scores corresponding to a greater level of anxiety or depression.

Missing items will be replaced by the mean of non-missing items from the same subscale when calculating the above, provided at least 50% of the items (ie, at least 4 of 7 items) within the subscale are present. A subscale score will not be calculated if more than 50% of the items are missing within a subscale. This rule applies separately to the subscale scores for anxiety and depression; for example, it may be possible to calculate the depression score in cases where the anxiety score is not calculated due to non-response.

### 10.2.1.8 Time to Discontinuation to Treatment

Time to discontinuation of treatment is calculated by the date of the last PSL dose minus the date of first dose +1.

### 10.2.1.9 Treatment satisfaction

The Treatment Satisfaction Questionnaire for Medication (TSQM)-9 is a 9-item questionnaire developed to provide a suitable measure of treatment satisfaction with medication (Bharmal et al, 2009). It has 5 to 7 Likert response options per item and consists of 3 subscales: effectiveness (3 items), convenience (3 items), and a global satisfaction scale (3 items).

The TSQM-9 was developed from the TSQM 1.42, which has an additional subscale that measures side effects (3 items) (Atkinson et al, 2004). Scores range from 0 (worst) to 100 (best). The questionnaire is administered at EOS or EDV Visit, respectively.

#### Effectiveness

1.How satisfied or dissatisfied are you with the ability of the medication to prevent or treat your condition?

#### Responses

1=Extremely dissatisfied to  
7=extremely satisfied

2. How satisfied or dissatisfied are you with the way the medication relieves your symptoms? 1=extremely dissatisfied to 7=extremely satisfied

3. How satisfied or dissatisfied are you with the amount of time it takes the medication to start working? 1=extremely dissatisfied to 7=extremely satisfied

### Convenience

4. How easy or difficult is it to use the medication in its current form? 1=extremely difficult 7=extremely easy

5. How easy or difficult is it to plan when you will use the medication each time? 1=extremely difficult 7=extremely easy

6. How convenient or inconvenient is it to take the medication as instructed? 1=extremely inconvenient 7=extremely convenient

### Global satisfaction

7. Overall, how confident are you taking this medication is a good thing for you? 1=Not at all confident 5=extremely confident

8. How certain are you that the good things about your medication outweigh the bad things? 1=not at all certain 5=extremely certain

9. Taking all things into account, how satisfied or dissatisfied are you with this medication? 1=extremely dissatisfied 7=extremely satisfied

## 10.2.2 Analysis of other efficacy variables

All summaries and listings provided for the efficacy variables are calculated on FAS unless noted otherwise.

### 10.2.2.1 Seizure frequency by 3-month interval over the Evaluation Period

The observed and the absolute change in 28-day adjusted seizure frequency of observable focal-onset seizures by the 3-month intervals over the Evaluation Period will be summarized by region in descriptive tables. The same summary will be repeated for the completer cohorts.

The observed and change from baseline in seizure frequency of Type IA1, IB, and IC seizures will be summarized separately by seizure type. Summary will be provided for the overall and by 3-month interval during the Evaluation Period. Summary will also be provided by 3-month interval for each completer cohort. The same summary will also be provided for the all Type I seizures.

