12.4.2 Analysis of the other efficacy variables

The following efficacy variables will be summarized with descriptive statistics:

- Observable focal-onset seizure frequency per 28 days by 3-month intervals over the Evaluation Period; the median will be considered as the key statistic
- Observable focal-onset seizure frequency per 28 days by seizure type and by 3-month intervals over the Evaluation Period; the median will be considered as the key statistic
- The 50%, 75%, and 90% RR by 3-month intervals or observable focal-onset seizures over the Evaluation Period. A 50%, 75%, and 90% responder is defined as a subject with a $\geq 50\%$, $\geq 75\%$, or $\geq 90\%$ reduction in observable focal-onset seizure frequency relative to the Baseline Period in the parent study.
- The 50%, 75%, and 90% RR by 3-month intervals for focal-onset (Type I) seizures over the Evaluation Period
- Percentage of seizure-free days (for all seizure types) by 3-month intervals over the Evaluation Period
- Seizure-freedom status for all seizure types by 3-month intervals over the Evaluation Period
- Change from Baseline from parent study in the Seizure Severity Global Item (SSG) scores at each assessment
- Changes from Baseline from parent study in QOLIE-31-P scores at each assessment
- Changes from Baseline from parent study in HADS scores at each assessment
- Changes in drug load (ie, number of products, daily dose per given product, ratio of dose and Defined Daily Dose [WHO Collaborating Centre for Drug Statistics Methodology], frequency, drug class) of AEDs from Baseline to Visit 8 and to Visit 12 or EOS

- Use of Health-related outcomes and HRU, including healthcare provider consultations not foreseen by protocol, caregiver support, concurrent medical procedures, concomitant medications and hospitalizations

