## 1 INTRODUCTION

This statistical analysis plan (SAP) defines the scope of statistical analyses and provides a detailed description of statistical methodology for the statistical analyses to support the final

clinical study report (CSR). The SAP is based on the following study document: Protocol EP0093 Amendment 2, 4 February 2020. All references to study protocol hereafter refer to this version of the protocol. Unless otherwise specified, the study will be analyzed as described in the most recent version of the protocol (EudraCT-Number: 2017-003241-26; IND number 135622). If a future protocol amendment necessitates a substantial change to the statistical analysis of the study data, or if analysis definitions must be modified or updated, this SAP will be amended accordingly. The content of this SAP is compatible with the International Council for Harmonisation of Technical Requirements for Pharmaceuticals for Human Use (ICH)/Food and Drug Administration (FDA) E9 Guidance documents (ICH E9, 1998).

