### 3.5.3 Full Analysis Set

The Full Analysis Set (FAS) will consist of all enrolled subjects who were administered at least 1 dose of PSL or a partial dose of PSL and completed at least 1 seizure diary during the Evaluation Period.

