### 4.1 Handling of dropouts or missing data

#### 4.1.1 Handling of missing data in seizure frequency

Seizure frequency will be calculated over non missing diary days during an analysis period or time interval. Days with missing seizure diary (ie, "Not Done" is ticked on the Seizure Count CRF) will not be considered in the calculation of seizure frequency or seizure free days. No imputation will be applied to missing seizure diary data. Seizure frequency during a time interval will be calculated if seizure data are available for at least 1 day during the interval.

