### 10.1 Statistical analysis of the primary efficacy variables

#### 10.1.1 Derivations of primary efficacy variable

Seizure frequency (SF) refers to the 28-day adjusted seizure frequency, which is defined as:

$$SF = (\text{Number of Seizures}) \times (28 / D)$$

- where Number of Seizures = total number of seizures during an analysis period or time interval. For cluster seizures, the number of cluster episodes will be included.
- D = number of days for which the diary was available during the analysis period or time interval.

Change from Baseline in seizure frequency will be calculated as seizure frequency during an analysis period or time interval minus the Baseline seizure frequency.

The primary efficacy variable is the change from Baseline in the observable focal-onset seizure frequency over the Evaluation Period.

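### Summarizing Type IA1, IB and IC frequency over the whole FAS makes the median, the protocol's key statistic, 0 for any type recorded by fewer than half of the subjects

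*SAP*

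**What the plan says.** - **Variable and key statistic.** Protocol 4.2.2 lists observable focal-onset frequency by seizure type among the other efficacy variables. Protocol 12.4.2 plans it "by seizure type and by 3-month intervals over the Evaluation Period; the median will be considered as the key statistic".
- **By-type tables.** SAP 10.2.2.1: "The observed and change from baseline in seizure frequency of Type IA1, IB, and IC seizures will be summarized separately by seizure type". These are planned overall, by 3-month interval and by completer cohort. Change from Baseline by type is an SAP addition.
- **Denominator.** SAP 10.2.2: "All summaries and listings provided for the efficacy variables are calculated on FAS unless noted otherwise". Section 10.2.2.1 notes no other population for the by-type tables except the completer cohorts, which SAP 3.2.6 defines by duration alone. FAS membership (SAP 3.5.3) needs a full or partial dose of PSL and that the subject "completed at least 1 seizure diary during the Evaluation Period". It sets no condition on seizure type.
- **Zero or missing.** SAP 4.1.1: "Seizure frequency during a time interval will be calculated if seizure data are available for at least 1 day during the interval". In SAP 10.1.1 the divisor D is the "number of days for which the diary was available during the analysis period or time interval", whatever types were recorded. The same section adds: "Change from Baseline in seizure frequency will be calculated as seizure frequency during an analysis period or time interval minus the Baseline seizure frequency".
- **Carry-over of the median.** SAP section 1: "Unless otherwise specified, the study will be analyzed as described in the most recent version of the protocol". The list of changes in SAP 3.9 does not touch the choice of median.

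**The concern.** A subject who never has a given type is not informative about the effect of PSL on that type, yet contributes a zero to each of its summaries. When such subjects are the majority, the median describes them and not the subjects with the type. The protocol's chosen statistic would then read 0 at Baseline, 0 in the interval and 0 for change, whether those seizures were abolished, halved or made worse. When they are a large minority, the median describes subjects with a low frequency and understates both burden and effect.

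No other by-type effect summary compensates. Percent reduction (SAP 10.2.2.6) and responder rates (SAP 10.2.2.2 and 10.2.2.3) are planned only for observable focal-onset seizures combined and for all Type I seizures. The lifetime seizure-type profile (SAP 6.3.2.1) is tabulated but is not used as a denominator.

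**Working it through.** The plan states no figure for this variable, so there is nothing to reproduce. The check is an order-statistic argument followed by illustrations. Shares, frequencies and effects are assumptions, because the documents give none of them.

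**1. Contribution of a subject without the type.** SF = count x 28/D. With count 0 and D of at least 1, SF = 0. Change = 0 - 0 = 0. The value is observed, not missing.

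**2. Type recorded by a minority.** Suppose fewer than half of the subjects record the type at Baseline, and fewer than half record it in the interval.
- More than half of the Baseline values are 0, and more than half of the interval values are 0, so both medians are 0.
- Only subjects with the type at Baseline can have a negative change: fewer than half.
- Only subjects with the type in the interval can have a positive change: fewer than half.
- The middle of the ordered changes is therefore 0, whatever the size of effect among subjects with the type.

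**3. Type recorded by a majority (share p above 0.5).** The whole-FAS median frequency is the (p - 0.5)/p quantile among subjects with the type. Assume that frequency is lognormal, with median 8 per 28 days and log-SD 1.2.
- p = 0.6: 0.1/0.6 = 0.167 quantile, 8 x exp(1.2 x -0.967) = 2.5, against 8.
- p = 0.8: 0.3/0.8 = 0.375 quantile, 8 x exp(1.2 x -0.319) = 5.5, against 8.

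**4. Change, with seizures typically halved.** Follow-up = Baseline x lognormal (median 0.5, log-SD 0.6). Medians are simulated. Mean change is p x 8 x exp(1.2²/2) x (0.5 x exp(0.6²/2) - 1) = p x 16.43 x (0.599 - 1) = p x -6.6.

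| Share with type | Median change, whole FAS | Median change, subjects with type | Mean change, whole FAS |
|---|---|---|---|
| 30% | 0 | -2.9 | -2.0 |
| 45% | 0 | -2.9 | -3.0 |
| 60% | -0.3 | -2.9 | -4.0 |
| 80% | -1.7 | -2.9 | -5.3 |

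**5. Same question with seizure counts.** 1000 subjects, Poisson counts, lognormal rates (median 8, log-SD 1), 28-day Baseline, 90-day interval.
- At shares of 20%, 30%, 40% and 45%, whole-FAS medians for Baseline, interval and change were 0, 0 and 0 for every effect tried: none, 50% reduction, 90% reduction, 50% worsening.
- The mean change did respond. At 45% it was -2.86, -5.50 and +3.13 for the last three effects.
- At 55%, median change was 0 for a 50% reduction and -1.22 for a 90% reduction, against -4.07 and -8.00 in subjects with the type.
- At 70%, a 50% reduction gave -1.44 against -4.02.

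**6. New onset.** 45% have the type at Baseline and their rate is halved; 5%, 10% or 20% of the others acquire it. The share recording the type in the interval was 46.9%, 49.8% and 55.4%. Median observed frequency was 0, 0 and 0.93. Median change was 0 in all three.

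**7. What selection at Baseline does.** Restricting to subjects with at least one Baseline seizure of the type makes the effect visible: in the step 5 setting at shares of 20% to 45%, median change is -3.7 to -4.6 for a 50% reduction. It also selects on a chance count. With **no** drug effect (Poisson counts, lognormal rates with log-SD 1.0 to 1.2, 28-day Baseline, 90-day interval), the selected group shows:

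| Median rate per 28 days | Median change | Median percent reduction |
|---|---|---|
| 0.5 | -0.69 | 38% |
| 1 | -0.38 | 22% |
| 8 | close to 0 | close to 0 |

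**The case against.** A reader might infer that the by-type tables cannot show benefit or worsening at all. The documents do not support that. Protocol 12.2 calls for mean, SD, standard error, median, minimum and maximum, and SAP 3.1 gives display rules for the mean, SD, median and range. The whole-FAS mean moves (step 4), although it is scaled down by a share that the table does not show. SAP 10.1.2 also plans a per-subject listing with seizure type and counts.

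A reader might also infer that all medians are 0 in every interval whatever PSL does. That goes too far. Each interval includes only subjects with diary data in it, so the mix can shift with dropout, and new onset can lift the observed median above 0 (step 6). The identity needs the type to be recorded by fewer than half at Baseline and fewer than half in the interval.

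Three further objections have weight:
- The protocol names the median as key for frequency, not for change, so the figures for median change illustrate an SAP addition.
- The share of subjects with each type is not given, so it cannot be said that IA1, IB or IC is in fact affected.
- The stakes are limited. This is one of several other efficacy variables in an open-label extension whose primary objective is safety, with no testing or modelling even of the primary efficacy variable. That variable and the other summaries based on combined seizure types are not affected in this way.

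These objections limit the point without removing it. The SAP cannot rely on every type being a majority type. Nothing in it tells the programmer to subset, and doing so unannounced would depart from SAP 10.2.2.

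**Conclusion.** The point stands as a defect of one planned summary. As written, the key statistic for by-type frequency carries no information on any type that fewer than half of the subjects record at Baseline and in the interval, and median change by type is 0 as well. Above half, both are pulled towards 0. That part is exact and needs no distributional assumption.

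The sizes (0 at 30% and 45%, about -0.3 at 60%, -1.7 at 80%, against -2.9) rest on the assumed lognormal frequencies and a typical halving. With the count-based assumptions of step 5 the contrast is larger, for example 0 against -4.07 at 55%. Which types are affected stays open until the shares are known. The change is worth making because it is cheap and the variable is listed in the protocol; it does not bear on the primary efficacy variable.

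**What to change.** In SAP 10.2.2.1, keep the planned whole-FAS tables and add beside them, for each of IA1, IB and IC:
- observed frequency and change, overall, by 3-month interval and by completer cohort, in FAS subjects with at least one seizure of that type in the parent-study Baseline, with n shown in each cell;
- separately, the number of subjects whose first recorded seizure of that type falls in the Evaluation Period, and their frequency, so that emergence is not lost.

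State in the same section that selecting on a 4-week Baseline count brings regression to the mean, that this is largest for infrequent types, and that there is no control group to separate it from a drug effect. Median change for infrequent types should be read with that caveat.

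Cost: a few sentences, one subset flag per type and extra table columns. No new data are needed, since change by type already requires Baseline counts by type. The downsides are a smaller n per type and the selection effect just described, which is why the whole-FAS table stays.

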#### **10.2.2.2 50%, 75% and 90% responder rates by 3-month interval for observable focal onset seizures over the Evaluation Period**

Summaries and listings for the 50%, 75% and 90% responder rates for observable focal-onset seizures will be provided for the overall Evaluation Period and by 3-month interval. Summaries will also be provided by 3-month interval for each completer cohort.

#### **10.2.2.3 50%, 75% and 90% responder rates for focal-onset seizures (all Type I) over the Evaluation Period**

Summaries for the 50%, 75% and 90% responder rates for all Type I seizures will be provided for the overall Evaluation Period and by 3-month interval. Summaries will also be provided by 3-month interval for each completer cohort.

#### **10.2.2.4 Seizure-freedom status for all seizure types by 3-month interval over the Evaluation Period**

The number and percentage of subjects achieving a seizure-free status will be summarized by 3-month interval for each completer cohort. After the study completion, the same summary will be performed for the overall and by 3-month interval for the Evaluation Period.

#### **10.2.2.5 Percentage of seizure-free days (for all seizure types) by 3-month interval over the Evaluation Period**

The percentage of seizure-free days and change from baseline in percentage of seizure-free days will be summarized for the overall Evaluation Period and by 3-month interval. Summaries will also be provided by 3-month interval for each completer cohort.

#### **10.2.2.6 Percentage of reduction in seizure frequency by 3-month interval over the Evaluation Period**

The percentage of reduction in seizure frequency from baseline for observable focal-onset seizures and all Type I seizures will be summarized for the overall Evaluation Period and by 3-month interval. Summaries will also be provided by 3-month interval for each completer cohort.

#### **10.2.2.7 Change in the SSG score**

Data will be listed for each scheduled visit and the Last Visit during the Evaluation Period by subject.

#### **10.2.2.8 Changes in the QOLIE-31-P score**

Observed values for QOLIE-31-P total score and subscale scores for Seizure Worry, Daily Activities/Social Function, Energy/Fatigue, Emotional Well-Being, Cognitive Function, Medication Effects, Overall Quality of Life, and Health Status will be listed for Visit 6, Visit 8, Visit 10 and EOS Visit.

For each time point, the change from baseline of the parent study will be listed by subject for total and subscales.

### 10.2.2.9 Change in Hospital Anxiety and Depression Scale (HADS) score

Changes in the HADS scores will be calculated from Baseline from parent study to Entry Visit, Visit 4, Visit 6 and to Visits every 3 months thereafter until EOS or EDV Visit. The observed scores and changes in the scores for depression and anxiety will be presented in a subject listing.

### 10.2.2.10 Health-related Outcomes and HRU

Health-related outcomes data and HRU data will be listed for the SS.

- Socio-professional status

Socio-professional status data are collected at Entry Visit and EOS/EDV. Variables include highest level of education, housing status, current professional status, current unemployed status, need for regular assistance due to epilepsy, and ability to drive.

- Healthcare provider consultations not foreseen by the protocol

Healthcare consultations by type of provider (general practitioner, specialist physician, nurse, and other) will be listed for each subject during the study.

- Hospital and ER visits

ER visits will be extracted from the Hospitalization/ER Visit CRF page (if the initial entry point is ER).

- Caregiver assistance

Caregiver assistance data is collected on the CRFs “Caregiver Assistance”.

- Number of school or working days lost

Number of school/working days lost data are collected on the CRFs “School and Workdays Lost”. The number and percentages of subjects who lose school or work days as a result of epilepsy will be listed by visit. The percentage of days lost will be calculated as:

$100 \times (\text{end date of absence} - \text{start date of absence} + 1) / (3 \times 30 + 1)$  for the Entry Visit. If the end date of absence is missing or after Entry Visit date, the end date of absence will be set to Entry Visit; if the start date of absence is missing or prior to Entry Visit-90, the start date of absence will be set to Entry Visit-90.

$100 \times (\text{end date of absence} - \text{start date of absence} + 1) / (\text{visit date of current visit} - \text{visit date of previous visit})$  for the later visits. If the end date of absence is missing or after the current visit date, the end date of absence will be set to the current visit date; if the start date of absence is missing or prior to the previous visit+1, the start date of absence will be set to the previous visit date+1.

If multiple absences are reported at a given visit, the sum of the duration of all absences will be used in the numerator.

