12.8 Determination of sample size

For this OLE study, no sample size calculation is needed. The sample size will depend upon recruitment into and completion of the previous study. Approximately 1000 subjects may be included.

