## 3.9 Changes to protocol-defined analyses

Due to the COVID-19 impact on site initiation and enrollment as well as early termination of the study, the following items in the protocol were updated in the SAP

Section in this SAP	Description	Change from the protocol
Table 2-1:	Schedule of Assessments	Added: Setting (Required Onsite) column to include data that may be collected through phone or video calls for visit, during the pandemic.

3.10	COVID-19 eCRF	Added, see section 3.10 for details
4.4	Examination of subgroups	Removed China as a region
10.2.1.8	Derivation of other efficacy variables	
Removed: Drug Loads of AEDs
 
Changes in drug load are captured by number of products and daily dose per given product recorded in the AED Medication CRF. Drug load will be assessed using ratio of actual daily dose and World Health Organization defined daily dose (DDD).  “https://www.whocc.no/atc_ddd_index/?code=N03A&showdescription=no”.
 
The daily dose of the administered AED will be calculated at Entry Visit, Visit 8, and EOS. All AEDs which has the stop date at the visit (EV, Visit 8, EOS) or ongoing and the start date prior to the visit will be considered administered at that specific visit.
 
The drug load of all AEDs will be calculated as the sum of ratios of dose and DDD for each of the AEDs at the respective visit. The drug load of each AED class will be calculated as the sum of ratios of dose and DDD for each of the AEDs within the AED class. AED classes included in this analysis are:
 
 
• SV2A: levetiracetam and brivaracetam
 
• BZD: ATC code N05BA
 
• sodium channel-blocking AED (SCB (+): carbamazepine, oxcarbazepine, eslicarbazepine, phenytoin and lamotrigine
 
 
Ratio of dose and DDD, absolute change from EV in the ratio, and percent change from EV in the ratio will be summarized by all AEDs, AED drug class and by each of the AEDs. For two visits, the absolute change of a given AED drug load can be calculated if the product is administered at one of the visits; and the percent change can only be calculated if the AED is administered at EV. The change in number of all AEDs at Visit 8 and EOS relative to EV will also be summarized.

11	COVID-19	The impact of COVID-19 global pandemic on this study is detailed in section 3.10. COVID-19 impact will be listed by

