#### 10.1.2 Primary analysis of the primary efficacy variable

The observed and the absolute change in 28-day adjusted observable focal-onset seizure frequency will be summarized (FAS) for the overall Evaluation Period. The summary will be repeated for each region. A per-subject listing (FAS) will be provided with details of seizure diary including type of seizure, cluster, number of seizures per diary. No additional statistical testing or modelling will be performed.

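### SAP 10.2.2.7 to 10.2.2.10 give only subject listings for SSG, QOLIE-31-P, HADS and most HRU items, contrary to protocol 12.4.2, and SAP 3.9 does not record the departure

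*SAP*

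**What the plan says.** Protocol 12.4.2 opens its list with "The following efficacy variables will be summarized with descriptive statistics". The list includes change from parent-study Baseline at each assessment for SSG, QOLIE-31-P and HADS. It also includes health-related outcomes and HRU, with five named components: unforeseen consultations, caregiver support, concurrent medical procedures, concomitant medications and hospitalizations. SAP 2.2.2.2 carries all four variables forward as other efficacy variables.

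The SAP's analysis sections then specify:

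- SSG (10.2.2.7): "Data will be listed for each scheduled visit and the Last Visit during the Evaluation Period by subject".
- QOLIE-31-P (10.2.2.8): observed scores are listed, and "the change from baseline of the parent study will be listed by subject for total and subscales".
- HADS (10.2.2.9): observed scores and changes "will be presented in a subject listing".
- HRU (10.2.2.10): "Health-related outcomes data and HRU data will be listed for the SS".

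Within 10.2.2.10, the school and work days item asks for numbers and percentages of subjects by visit, but says these will be listed.

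SAP 3.9 introduces its table of departures by saying that, because of COVID-19 and early termination, "the following items in the protocol were updated in the SAP". Its rows cover the schedule of assessments, the COVID-19 eCRF, the dropped China region, AED drug load, COVID-19 impact and the Japan addendum. The change from summaries to listings is not among them.

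**The concern.** A listing shows each subject's values and gives no mean, median, proportion or average change. If the SAP is followed as written, the report will have no group-level statement on severity, quality of life, or anxiety and depression. It will have very little on resource use. SSG, QOLIE-31-P and HADS are efficacy variables, so their loss falls on the secondary objective of long-term efficacy. The exploratory objective is specifically about health-related outcomes and HRU, so the HRU losses fall there.

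Traceability is also affected. SAP section 1 says the study is analyzed as in the protocol unless otherwise specified, and 3.9 is where a reader would look for departures. Because 3.9 declares the drug-load removal, its silence on these four variables suggests that they are handled as the protocol says. SAP section 15 repeats only tables for Japan and non-Japan, so variables that are only listed get no result in those subgroups either.

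**Working it through.** No power or precision calculation applies. Protocol 12.8 states "For this OLE study, no sample size calculation is needed", and SAP 10.1.2 says of the primary efficacy variable that "No additional statistical testing or modelling will be performed". The check is a comparison of current texts, variable by variable.

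**Step 1. The twelve other efficacy variables (protocol 4.2.2).**

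| Variable | Current SAP output |
|---|---|
| Six seizure-diary variables: frequency, frequency by type, two sets of responder rates, seizure-free days, seizure freedom | Summarized (10.2.2.1 to 10.2.2.5) |
| Time to discontinuation | Kaplan-Meier estimates (10.2.2.11) |
| SSG | Listing only |
| QOLIE-31-P | Listing only |
| HADS | Listing only |
| AED drug load | Removed, declared in 3.9 |
| HRU | Mostly listing |

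Count: 6 + 1 = 7 keep their summaries, 3 lose all of them, 1 is removed and declared, and 1 is mostly reduced. 7 + 3 + 1 + 1 = 12.

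**Step 2. HRU item by item (the seven items of protocol 10.5).**

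| Item | Current SAP output |
|---|---|
| Healthcare provider consultations | Listing |
| Hospitalizations and ER visits | Listing |
| Caregiver support | Listing |
| Socio-professional status | Listing |
| Concurrent medical procedures | No entry in 10.2.2.10 |
| Concomitant medications | Number and percentage of subjects (6.4.1, 6.4.3) |
| School or work days lost | Number and percentages of subjects by visit, described as listed |

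Five of the seven items have no summary, one is summarized, and one is ambiguous. Of the five components named in protocol 12.4.2, four have no summary and one (concomitant medications) does.

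**Step 3. Does the protocol mean a summary when it says so?** Protocol 12.3 specifies listings where it wants them: physical and neurological examinations, psychiatric assessments, CIWA-B and C-SSRS. The protocol therefore distinguishes the two outputs, and it placed these four variables among those to be summarized.

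**Step 4. Is there a table elsewhere?** The rest of the SAP contains no group-level output for SSG, QOLIE-31-P or HADS. For HRU, the only ones are the two in step 2.

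**The case against.** The strongest reply is that the change was open and proportionate. SAP Amendment 1, Changes #43 to #46, shows the summaries being withdrawn variable by variable. The amendment's rationale cites early termination of the study. This is a single-arm, open-label extension with no hypothesis tests, and these are not primary variables. Cutting output after early termination can be reasonable.

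Much of that stands. A reader who sees the gap in 3.9 might infer that the change was concealed, and the amendment log rules that out. The log, however, compares SAP versions; it does not declare a departure from the protocol, which is the purpose of 3.9. The early-termination rationale is general. It does not explain why these variables lose their tables while seizure frequency, responder rates and seizure-free days are still tabulated overall, by 3-month interval and by completer cohort. A smaller sample does not prevent descriptive statistics.

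Two other readings go too far. A reader of 10.2.2.10 alone might conclude that every HRU item is reduced to listings and that the exploratory objective has no group-level result at all. SAP 6.4.1 and 6.4.3 contradict this for concomitant medications. The natural reading of the school and work days sentence is a group-level quantity loosely described as listed, not a contradiction. A reader might also count SSG, QOLIE-31-P and HADS as losses to the exploratory objective, but protocol 10.5 does not place them under health-related outcomes and HRU. Finally, the documents do not show that report authors would pick selectively from the listings.

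**Conclusion.** The departure from protocol 12.4.2 is real and SAP 3.9 does not record it. SSG, QOLIE-31-P and HADS, three of the 12 other efficacy variables, lose all summary statistics, which weakens reporting on the secondary efficacy objective. HRU loses most of its summaries, which leaves the exploratory objective with almost no group-level result. The primary safety variables and the primary efficacy variable are not affected.

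This conclusion rests on reading listed as a per-subject listing in 10.2.2.7 to 10.2.2.10, and on treating the school and work days sentence as an intended table. If that sentence also means a listing, concomitant medications would be the only HRU item still summarized.

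**What to change.** 1. In SAP 10.2.2.7 to 10.2.2.9, restore descriptive tables by visit of the observed value and change from parent-study Baseline for SSG, QOLIE-31-P (total and subscales) and HADS (anxiety and depression). The second SSG item is itself a rating of change, so counts per category are enough for it.
2. In SAP 10.2.2.10, add counts and percentages for the HRU categories (consultations, hospitalizations and ER visits, caregiver support, socio-professional status), and add an entry for concurrent medical procedures.
3. Reword the school and work days sentence so that the numbers and percentages of subjects are tabulated by visit.
4. Record and justify in SAP 3.9 any table that is still dropped.

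A suggested addition, which protocol 12.4.2 does not itself require, is a Last Visit row under the existing SAP 3.2.4 rule. SAP 3.2.3.1 leaves questionnaires from the Early Discontinuation Visit (EDV) unmapped, and 10.2.2.8 names only Visits 6, 8, 10 and EOS for QOLIE-31-P although it is also collected at the EDV. After early termination, a table restricted to scheduled visits could miss exit assessments. The SAP 3.2.4 rule takes the last non-missing value up to the last dose, so the text should say how an EDV after the last dose is handled.

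The cost is SAP wording and a few extra standard tables, each repeated for Japan and non-Japan under SAP section 15. The data are already collected, and the QOLIE-31-P and HADS changes are already derived for the listings.
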